8.2.3.2. Adverse events

- **All adverse events**

Number and proportion of patients with adverse events will be tabulated by SOC and PT.

- **Adverse events by serious/non-serious**

Number and proportion of patients with serious adverse events will be tabulated by SOC and PT. Non-serious adverse events will be tabulated in the same manner.

8.2.3.3. Other endpoints

- **Body weight**

Summary statistics specified in Section 8.1.1 will be calculated by time point as defined in Appendix 1 for measurements and their changes from baseline.

Number and proportion of patients with the following adverse reactions will be tabulated for patients whose body weight increased by 7% or more from baseline at least once and other patients.

- Abnormal glucose tolerance-related events: Events coded to the MedDRA HLGT “glucose metabolism disorders (incl diabetes mellitus)” or the MedDRA HLT “carbohydrate tolerance analyses (incl diabetes)”
- Dyslipidemia-related events: Events coded to the MedDRA HLGT “lipid metabolism disorders” or “lipid analyses”
- Events coded to the MedDRA PT “arrhythmia”, “atrial fibrillation”, “cardiovascular disorder”, “cardiac failure congestive”, “hypertension”, “hypotension”, “palpitations”, “tachycardia”, or “dyspnoea”
- Events coded to the MedDRA SOC “Cardiac disorders”, “Vascular disorders”, or “Respiratory, thoracic and mediastinal disorders”

- **Laboratory parameters**

Summary statistics specified in Section 8.1.1 will be calculated by time point as defined in Appendix 1 for laboratory parameters and their changes from baseline.

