5.1. Safety analysis set

The safety analysis set is the full analysis set that is as close to all patients treated with Lyrica as possible. More specifically, the safety analysis set is defined as the population of registered or reported patients, excluding those who meet any of the following conditions.

- a. The survey form could not be collected at all (description in the report: “survey form not collected”).
- b. There was a contract violation or deficiency (description in the report: “contract violation/deficiency”).
- c. There was a registration violation (description in the report: “registration violation”).
- d. Administration of Lyrica under survey has not been reported at all (description in the report: “no administration information”).
- e. Information on adverse events has not been reported at all - no visits after the day of initial prescription (description in the report: “no adverse event information - no revisit”).
- f. Information on adverse events has not been reported at all - adverse events not described (description in the report: “no adverse event information - not described”).

Detailed handling of patient inclusion in/exclusion from the analysis set should be in accordance with patient inclusion/exclusion criteria separately specified.

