6.4. Covariates

For safety and efficacy of Lyrica, no covariates or potential covariates are identified from clinical study data, etc. obtained to date.

7. Handling of missing data

If the seriousness/outcome of adverse events and action taken with Lyrica for the adverse events are missing, they will be handled as “unknown” at tabulation.

If body weight is not measured within the acceptable range at each time point (Appendix 1), it will be handled as missing and will not be imputed.

If there is no data of pain score and sleep interference score, it will be handled as missing and will not be imputed in “Week 4” and “Week 13” assessments. If data is missing at Week 13, it will be imputed with the data obtained at the last time point post-dose in “Week 13 LOCF” assessment.

8. Statistical methods and statistical analyses

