For “peripheral edema and edema-related events”, number and proportion of patients with events will be tabulated by presence or absence of weight increase. Two types of definitions of patients with weight increase are used: 1) those with “weight increased (MedDRA PT)” reported as an adverse reaction; 2) those with body weight increased by 7% or more from baseline at least once. Number and proportion of patients with adverse reactions will be tabulated for each SOC and PT by presence or absence of peripheral edema. In addition, number and proportion of patients with the following adverse reactions will be tabulated by presence or absence of peripheral edema to evaluate the relationship between peripheral edema and cardiovascular and respiratory events.

- Events coded to the MedDRA PT “arrhythmia”, “atrial fibrillation”, “cardiovascular disorder”, “cardiac failure congestive”, “hypertension”, “hypotension”, “palpitations”, “tachycardia”, or “dyspnoea”
- Events coded to the MedDRA SOC “Cardiac disorders”, “Vascular disorders”, or “Respiratory, thoracic and mediastinal disorders”

For “dizziness, somnolence, loss of consciousness, syncope, and potential for accidental injury”, number of days to onset will be tabulated using more specific categories (≤ 4 weeks [1 to 28 days], 1 to 7 days, 8 to 14 days, 15 to 21 days, 22 to 28 days; >4 weeks [≥ 29 days], >4 to ≤ 13 weeks, >13 weeks). In addition, number and proportion of patients with adverse reactions will be tabulated by factor specified in Section 5.4. Tests specified in Section 8.1.3 will be performed to evaluate the relationship between patient demographics, etc. and development of adverse reactions.

Moreover, the median number of days to onset will be tabulated for the following adverse reactions.

- Dizziness
- Somnolence

^a: Occurrence of cardiovascular and respiratory events will be examined in patients with peripheral edema and edema-related events.

- Peripheral edema and edema-related events
- **Pancreas-related events, thyroidal function-related events, change in appetite and activity-related events, suicide-related events, withdrawal symptom and rebound phenomenon-related events, and skin disorder-related events**

Number and proportion of patients will be calculated for each event.

- **Patients with special background**

Number and proportion of patients with adverse reactions and serious adverse reactions will be calculated by SOC and PT in the following subgroups and other patients.

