10.1. Appendix 1: Details of data extraction

A1.1 Data to be used for tabulation and analysis

Data collected after the safety evaluation date will not be used in tabulation and analysis specified in this plan. Data on efficacy endpoints (Section 6.2) will be used even if they are collected after the safety evaluation date.

A1.2 Definition of visit schedule

Visit schedule	Endpoint	Definition [acceptable window]
Start of treatment	Laboratory tests and body weight	From 30 days before the first dose (date of start of treatment) in the survey to the date of start of treatment (Day 1)
After 4 weeks	Laboratory tests and body weight	Day 29 [Day 2 to Day 60]
After 13 weeks	Laboratory tests and body weight	Day 92 [Day 61 to Day 137]

If multiple data are collected within the acceptable window, the data whose date of evaluation is closer to the definition will be used for tabulation and analysis. If the difference from the definition is the same, the newer data will be used.

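### As worded, the 7% weight-gain tables place patients with no usable weight pair in the no-gain group; the resulting bias is of unknown size and can go either way

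*SAP*

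**What the plan says.** SAP 8.2.3.3 (Body weight) asks for the number and proportion of patients with glucose-related, lipid-related, and cardiovascular or respiratory adverse reactions in two groups: "patients whose body weight increased by 7% or more from baseline at least once and other patients".

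SAP 8.2.3.1 (Major investigation items) does something similar for edema: "number and proportion of patients with events will be tabulated by presence or absence of weight increase". It uses two definitions of weight increase. Definition 1 is a reported adverse reaction coded to the PT 'weight increased'. Definition 2 is "those with body weight increased by 7% or more from baseline at least once".

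Three other places bear on who falls in which group:

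- SAP 5.1 describes the population this way: "The safety analysis set is the full analysis set that is as close to all patients treated with Lyrica as possible". None of its exclusions, a to f, concerns a missing weight.
- SAP Section 7 says: "If body weight is not measured within the acceptable range at each time point (Appendix 1), it will be handled as missing". It adds that no imputation is made.
- SAP Appendix 1 (A1.2) sets the weight windows: 30 days before the first dose up to Day 1 for baseline, Day 2 to Day 60 for Week 4, and Day 61 to Day 137 for Week 13.

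**The concern.** Whether a patient gained 7% or more can be known only if there is a baseline weight and at least one later weight. The comparator in 8.2.3.3 is a pure complement, and the edema table offers only presence or absence. Neither has a place for a patient whose status is unknown, so the wording sends that patient to the no-gain side.

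These tables are the SAP's look at whether measured weight gain accompanies edema (a major investigation item), glucose and lipid reactions, and cardiorespiratory reactions. If unweighed patients differ from weighed patients in their recorded reaction rate, the no-gain proportion is not that of patients who did not gain. The share of patients shown as gainers is also too low whenever the denominator includes people who could not be assessed.

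**Working it through.** **Following the text.** A patient in the safety set without a usable weight pair passes through the SAP as follows. SAP 5.1 keeps the patient in. Section 7 makes the weight at that time point missing, which removes the patient from the by-visit summaries but says nothing on group membership. SAP 8.2.3.3 then asks whether a 7% gain was observed; it was not, so the patient is an 'other' patient. Under definition 2 of 8.2.3.1 the same patient falls under absence. Definition 1 needs no weights and is unaffected.

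**Size.** The documents give no figure for these tables, so there is nothing to reproduce. Every rate below is an assumption:

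- g = 8%: share gaining 7% or more
- event rate 10% in gainers and 4% in non-gainers, so the true risk ratio is 10/4 = 2.5
- m = 30% or 50%: share without a usable weight pair
- k = 0.3, 0.5, 1 or 1.5: recorded event rate in unmeasured patients relative to measured patients overall

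The overall rate in measured patients is 0.08 × 10 + 0.92 × 4 = 4.48%.

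Comparator rate = [(1 − m)(1 − g) × 4% + m × k × 4.48%] / [(1 − m)(1 − g) + m]; apparent ratio = 10% / comparator rate.

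The denominator is 0.7 × 0.92 + 0.3 = 0.944 at m = 30% and 0.5 × 0.92 + 0.5 = 0.96 at m = 50%. Unmeasured patients then make up 0.3/0.944 = 32% or 0.5/0.96 = 52% of the comparator.

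| k | m = 30%: comparator rate, ratio | m = 50%: comparator rate, ratio |
|---|---|---|
| 0.3 | (2.576 + 0.403)/0.944 = 3.16%, 3.17 | (1.84 + 0.672)/0.96 = 2.62%, 3.82 |
| 0.5 | (2.576 + 0.672)/0.944 = 3.44%, 2.91 | (1.84 + 1.12)/0.96 = 3.08%, 3.24 |
| 1 | (2.576 + 1.344)/0.944 = 4.15%, 2.41 | (1.84 + 2.24)/0.96 = 4.25%, 2.35 |
| 1.5 | (2.576 + 2.016)/0.944 = 4.86%, 2.06 | (1.84 + 3.36)/0.96 = 5.42%, 1.85 |

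If the reduced rate is scaled from the 4% non-gainer rate instead of 4.48%, the highest value becomes 10 / [(1.84 + 0.5 × 0.3 × 4)/0.96] = 10/2.54 = 3.93. The range is therefore roughly 1.85 to 3.9.

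**Second set of assumptions.** With event rates of 4% and 2% (true ratio 2.00), g of 5-10% and m of 10-50%, the apparent ratio is 2.10-2.64 at k = 0.5, 1.90-1.99 at k = 1, and 1.49-1.89 at k = 1.5. The pattern is the same: little change when missingness is unrelated to risk, and a shift either way when it is not.

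**Share shown as gainers.** With all patients in the denominator, the assumed 8% appears as 0.7 × 8 = 5.6% at m = 30% and 0.5 × 8 = 4.0% at m = 50%.

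**The case against.** The SAP nowhere states that an unmeasured patient counts as a non-gainer. Section 7 forbids imputing a missing weight, and calling such a patient 'no gain' comes close to imputing one, so a programmer might exclude these patients. That reading is possible, but Section 7 speaks of the value at a time point and not of these groups. If it is the intended reading, the tables still need to say so.

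A reader might also infer that the unmeasured are mainly early stoppers with few recorded reactions, so that the tables overstate the link with weight gain. The documents do not support that:

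- SAP 5.1 item e already removes patients who never returned and have no adverse event information.
- The Week 4 window opens on Day 2, and Protocol 6.4 also asks for a weight by the day of safety evaluation, so many early stoppers could have a usable weight.
- Protocol 5.4 gives stoppers 7 days of follow-up.
- Protocol 5.3 says adverse events were most frequent early in treatment, and Protocol 6.6 lists them as a reason for stopping. Unweighed stoppers may thus have more recorded reactions, not fewer.

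Two further points limit the consequence. These weight tables call for counts and proportions only; the planned risk ratios and tests attach to the factors in SAP 5.4, and weight gain is not one of them. Nor is evaluability wholly hidden: the by-visit summaries in 8.2.3.3 include the number of patients, and a listing of body weights is planned. What is missing is the count of patients evaluable at either visit, shown beside the event table.

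**Conclusion.** The point holds as a gap in the definition. On the literal wording, 8.2.3.3 and definition 2 of 8.2.3.1 combine 'did not gain' with 'not weighed', and no other section corrects this.

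Neither a direction nor a size can be asserted. Under the assumed rates, a true ratio of 2.5 could appear as anything from about 1.85 to 3.9 with 30-50% unmeasured, and as 2.35-2.41 if being unmeasured is unrelated to risk. The 30-50% share and all event rates are illustrative. The ratio serves only to gauge the distortion, since the plan does not compute one here.

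The tables are descriptive and SAP 4.1 declares testing in the survey exploratory, so this is a minor improvement and not a threat to any main conclusion. By-visit weight summaries and the definition 1 tabulation stand as they are.

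**What to change.** In SAP 8.2.3.3 and for definition 2 in 8.2.3.1:

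- Classify gain of 7% or more (yes or no) only in patients with a baseline weight and at least one post-baseline weight.
- Apply the same Appendix 1 window rule to gainers and non-gainers, and state whether 'at least once' refers to every post-baseline weight in the windows or only to the one selected per window. If the rule bound only the comparator, an out-of-window weight could make a patient a gainer but never a non-gainer.
- Report all remaining patients, with their event counts, in a separate 'weight not evaluable' column, so that no reaction drops out of view.

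This follows the SAP's own practice elsewhere: Section 7 gives missing seriousness and outcome an 'unknown' category, and the response rate in 8.2.4.1 counts only patients judged effective or ineffective.

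The cost is a sentence or two and one extra column, with no new data. The downside is a smaller comparator. At the target of 3400 patients and the assumed 8% gain, it would be 3400 × 0.644 ≈ 2190 instead of 3400 × 0.944 ≈ 3210 with 30% unmeasured, or 3400 × 0.46 = 1564 instead of 3400 × 0.96 = 3264 with 50%.

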## 6.8 Adverse events

For evaluation of safety, the incidence of adverse events following the start of treatment with the product will be checked, and the following information will be entered. If any adverse event occurs, the investigator should take appropriate measures and immediately report it to the sponsor. When the causal relationship between the event and the product cannot be ruled out, observe the course of event or its sequela until they disappear or become stabilized at the level acceptable for the investigator and the sponsor.

A detailed investigation will be separately carried out if patients have intrauterine exposure or develop serious adverse reactions, adverse reactions not listed in the package insert and the like and the sponsor deems it necessary.

- [1] Day of safety evaluation (as a rule, day of last visit within 29 days after the start of treatment)
- [2] Presence/absence of adverse events
- [3] Name of adverse event
- [4] Date of onset
- [5] Measures taken

- [6] Seriousness
- [7] Outcome
- [8] Causal relationship to the product

[The following information should be entered if the adverse event is associated with abnormal changes in test data such as laboratory tests.]

- [1] Name of test
- [2] Reference value at the facility
- [3] Unit
- [4] Date of measurement
- [5] Results

Supplementary note: Adverse events mean all events unfavorable for the patient, arising after the start of treatment with the product, regardless of presence/absence of causal relationship to the product (including clinically significant abnormal changes in laboratory parameters). Serious adverse events mean death, life-threatening events, and events possibly causing hospitalization, extension of hospital stay period, permanent or marked disorders/disabilities, congenital anomalies/defects or other medically significant events/disorders.

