## 6.9 Major investigation items

The following events should be evaluated as major investigation items in this survey.

- [1] Peripheral edema and edema-related events
 

Information will be collected about the presence/absence of events related to peripheral edema and the course of patients before and after the onset of events. The situations on development of these events will be analyzed by means of factor analysis, including analysis of the site affected, dose of the product, concomitant therapy, background variables, etc. The package insert gives precautions on congestive heart failure in patients presenting symptoms related to edema. In 30 overseas placebo-controlled studies, the incidence of hypertension and dyspnea was higher in the patients developing peripheral edema than in patients free of peripheral edema, although the incidence of the other events did not differ markedly between these two groups. In view of these facts, information on cardiac function and the incidence of adverse events of the respiratory system will be also collected.
- [2] Dizziness, somnolence, loss of consciousness, syncope and potential for accidental injury
 

Information will be collected about the presence/absence of events related to dizziness, somnolence, loss of consciousness, syncope and potential for accidental injury and the course of patient's condition before and after the onset of events. The situations on development of these events will be analyzed by factor analysis, including analysis of the dose of the product, concomitant therapy, background variables and so on.
- [3] Vision-related events
 

Information will be collected about the presence/absence of events related to the eyes and the course of patient's condition before and after the onset of events. The situations on development of the events will be analyzed by factor analysis, including analysis of the dose of the product, concomitant therapy, background variables and so on.

Patients developing adverse events included in the major investigation items will be

separately investigated in detail if the sponsor deems it necessary.

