6.1. Safety endpoints

- Adverse reactions: Adverse events determined to be related to Lyrica by the investigator or the sponsor
- Adverse events: All-causality adverse events
- Serious adverse reactions or adverse events: Adverse reactions or adverse events determined to be serious by the investigator or the sponsor
- Major investigation items:
 - Peripheral edema and edema-related events*
*: Adverse events of the cardiovascular and respiratory systems will also be checked.
 - Dizziness, somnolence, loss of consciousness, syncope, and potential for accidental injury

- Vision-related events

Events to be handled as major investigation items are defined as events of safety specification in the European risk management plan of Lyrica (important identified risk: peripheral edema and edema-related events; dizziness, somnolence, loss of consciousness, syncope, and potential for accidental injury; vision-related events).

- Accident-related events:

Accident-related events are defined as events coded to the MedDRA SMQ “accidents and injuries”. These events will be evaluated for adverse events.

- Pancreas-related events:

Pancreas-related events are defined as events coded to the MedDRA SMQ “acute pancreatitis (narrow scope)”, those coded to the MedDRA HLGT “exocrine pancreas conditions” or the MedDRA HLT “pancreatic neoplasms malignant (excl islet cell and carcinoid)”, and those related to the laboratory test results of primary pancreatic parameters of serum amylase, lipase, and trypsin among those coded to the MedDRA SOC “Investigations”.

- Thyroidal function-related events:

Thyroidal function-related events are defined as events coded to the MedDRA SMQ “thyroid dysfunction”.

- Change in appetite and activity-related events

Change in appetite and activity-related events are defined as events coded to the MedDRA PT “decreased activity”, “decreased appetite”, “increased appetite”, or “hypokinesia”.

- Euphoric mood-related events:

Euphoric mood-related events are defined as events coded to the MedDRA PT “euphoric mood”.

- Suicide-related events:

Suicide-related events are defined as events coded to the MedDRA SMQ “suicide/self-injury”. These events will also be evaluated for adverse events.

- Withdrawal symptom and rebound phenomenon-related events:

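### In the 7% weight-gain comparison, the cardiovascular/respiratory event sets have no test-finding terms, although the glucose and lipid sets in the same list do

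*SAP*

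**What the plan says.** SAP 8.2.3.3 (Body weight) lists four groups of adverse reactions to be tabulated for patients with a weight gain of 7% or more and for other patients.

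- **Glucose:** a disorder group at MedDRA high-level group term (HLGT) level, "or the MedDRA HLT “carbohydrate tolerance analyses (incl diabetes".
- **Lipids:** "Events coded to the MedDRA HLGT “lipid metabolism disorders” or “lipid analyses".
- **Cardiovascular/respiratory, by preferred term (PT):** nine terms. The first three are arrhythmia, atrial fibrillation and cardiovascular disorder; the rest are "cardiac failure congestive”, “hypertension”, “hypotension”, “palpitations”, “tachycardia”, or “dyspnoea".
- **Cardiovascular/respiratory, by system organ class (SOC):** "Events coded to the MedDRA SOC “Cardiac disorders”, “Vascular disorders”, or “Respiratory, thoracic and mediastinal disorders".

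SAP 8.2.3.1 (Major investigation items) uses the same two cardiovascular/respiratory sets by presence or absence of peripheral edema. It also plans a table of all adverse reactions by SOC and PT for the same split.

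SAP 6.1 defines pancreas-related events by disorder groupings plus "laboratory test results of primary pancreatic parameters of serum amylase, lipase, and trypsin among those coded to the MedDRA SOC “Investigations".

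Protocol 6.8 defines adverse events as "including clinically significant abnormal changes in laboratory parameters", and its form has a block for events tied to abnormal test data. Protocol 6.9 states that "information on cardiac function and the incidence of adverse events of the respiratory system will be also collected".

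**The concern.** One clinical problem can be reported as a diagnosis or as a test result, and the two reports may be coded to different MedDRA classes. The SAP allows for this for pancreas, glucose and lipids, but not for the cardiovascular/respiratory sets, and it gives no reason for the difference.

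At stake is a grouped patient count. The set is meant to show whether weight gain, or edema, goes with cardiovascular or respiratory reactions. If some of those reactions are recorded only as test findings, the count is too low. If the share recorded that way differs between the two groups, the comparison is also distorted.

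**Working it through.** The plan states no figure for these sets, so the check is a comparison of definitions.

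**1. What each set contains**

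| Event set | SAP section | Disorder or symptom terms | Test terms |
|---|---|---|---|
| Pancreas | 6.1 | yes | yes, SOC Investigations named |
| Glucose | 8.2.3.3 | yes | yes, read from the word analyses in the group name |
| Lipids | 8.2.3.3 | yes | yes, read from the word analyses in the group name |
| Cardiovascular/respiratory, nine PTs | 8.2.3.1, 8.2.3.3 | yes | none |
| Cardiovascular/respiratory, three SOCs | 8.2.3.1, 8.2.3.3 | yes | none |

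No other section brings cardiovascular or respiratory test findings back into the last two sets.

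**2. Can such reports arise?** Yes. Protocol 6.8 counts clinically significant laboratory changes as adverse events, and its block for test-related events is not limited to the six laboratory parameters in Protocol 6.4(4).

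**3. Where would a test-coded reaction still be visible?**

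- Overall: in the SOC/PT tables of 8.2.3.1 and 8.2.3.2, without a split by edema or weight gain.
- By edema status: in the SOC/PT table of 8.2.3.1, one term per row. A patient can have several terms, so these rows do not add up to a patient count for the set.
- By 7% weight gain: in no table. Section 8.2.3.1 uses weight increase only to split edema events. The body-weight factor in 5.4 is weight at the start of treatment, not gain.

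**4. Size.** The documents do not say what share f of cardiovascular/respiratory reactions is recorded only as test findings. For illustration, assume true proportions of 4% and 2% in the two groups. The observed proportion is the true proportion × (1 − f).

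| f, equal in both groups | Observed proportions | Risk difference | Risk ratio |
|---|---|---|---|
| 0 | 4.0% v 2.0% | 2.0 points | 2.0 |
| 10% | 3.6% v 1.8% | 1.8 points | 2.0 |
| 20% | 3.2% v 1.6% | 1.6 points | 2.0 |
| 30% | 2.8% v 1.4% | 1.4 points | 2.0 |

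With equal f the risk difference shrinks by the factor (1 − f) and the ratio is unchanged. With unequal f the ratio moves too:

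- f = 30% and 10%: (4 × 0.7)/(2 × 0.9) = 2.8/1.8 = 1.56.
- f = 10% and 30%: (4 × 0.9)/(2 × 0.7) = 3.6/1.4 = 2.57.

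All inputs in this step are assumed. It shows the direction of the effect and does not estimate its size in this survey.

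**The case against.** The case for leaving the sets alone has real weight.

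- **The edema comparison is largely covered.** A reader might infer that test-coded events are lost from the analysis altogether. The documents do not support that: the SOC/PT table by edema status shows every such term, and the overall tables show them for the whole survey. Only the combined count is missing. This part of the objection stands.
- **The protocol ties cardiovascular and respiratory checking to edema, not to weight gain.** Protocol sections 1, 6.4(2) and 6.9 all do so. The weight-gain table goes beyond what the protocol asks, carries no test, and sits in a plan whose testing is exploratory (SAP 4.1) with no decision rule (4.2). This stands and limits the importance of the point.
- **Other sets also lack test terms.** Skin, appetite/activity and euphoric mood are defined by one SOC or by PTs alone. One cannot say that the cardiovascular/respiratory sets are the only exception to a SAP-wide rule. The narrower contrast, with the two bullets directly above in the same list, remains.
- **Test groupings may follow the tests collected.** Amylase, fasting glucose and HbA1c are survey items; blood pressure and ECG are not. This explains only part of the pattern, because lipids, lipase and trypsin are not among the six listed parameters either.
- **It is tempting to infer that test-coded reports cluster in edema patients.** Protocol 6.4(2) asks sites that find edema to check for cardiovascular and respiratory adverse events, but it orders no tests. The sentence on cardiac function in Protocol 6.9 concerns collection and defines no event set. Clustering is possible but not shown.
- **The listings could be searched.** Adverse reactions and body weights are both listed (SAP 9), so a missed case could be found by hand. That does not replace a defined count.

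**Conclusion.** The point holds for the 7% weight-gain comparison in SAP 8.2.3.3. As defined, its cardiovascular/respiratory sets cannot count a patient whose only such reaction is coded as a test finding, and no planned table by weight-gain status shows that reaction. For the edema comparison in 8.2.3.1 the point reduces to an incomplete combined patient count.

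The conclusion assumes that cardiovascular and respiratory test findings are coded outside the three disorder SOCs. The documents show test results coded to Investigations only for the pancreas, so this should be confirmed in the MedDRA version in use. The size of the undercount cannot be derived from the documents and may be nil. No primary result of the survey is affected. This is a cheap improvement, not a flaw that threatens a conclusion.

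**What to change.** Keep both existing sets unchanged as the first rows. In 8.2.3.3, add a row that counts each patient once if they have a reaction in the three SOCs or a cardiac, vascular (including blood pressure and heart rate) or respiratory test-finding term in SOC Investigations. Add the same row in 8.2.3.1 for the combined count by edema status.

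Fix the term list in the SAP. Draw it from the dictionary and not from the terms reported, because the survey is already complete at SAP version 8.0, and label the row as added after completion. If the exclusion was intended, one sentence giving the reason would serve instead.

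The cost is one line in each section, a term list and a rerun on data already coded; nothing new is collected. The downside is that test-coded terms are less specific, so the rows with and without them should stand side by side.
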